This study is performed as part of the Marketing Authorization Holder's post-marketing pharmacovigilance plan to investigate the long-term safety, in particular the diabetogenic potential and immunogenicity of recombinant human growth hormone (rhGH) therapy in short children born small for gestational age (SGA). Children born SGA who were treated in study EP00-401 with growth hormone due to short stature will be followed up for 10 years after stop of rhGH treatment. Patients will be monitored for safety.

2 Statistical and analytical plans

Data will be analyzed [REDACTED] according to this statistical analysis plan.

2.1 Study documents and general considerations

This document describes the procedures and conventions to be used in the final analyses with data of all patients who were included into study EP00-402.

The study is based on the

- study protocol V 1.0, dated 16 Mar 2007,
- Amendment no. 01, dated 12 Mar 2012 incorporated into protocol v 1.0 leading to protocol v 2.0, dated 12 Mar 2012,
- Amendment no. 02, dated 9 May 2012 incorporated into protocol v2.0 leading to protocol v3.0, dated 9 May 2012,
- Amendment no. 03, dated 6 Jun 2013 incorporated into protocol v3.0 leading to protocol v 4.0, dated 6 Jun 2013,
- Amendment no. 04, dated 14 July 2014 incorporated into protocol v4.0 leading to protocol v5.0, dated 14 July 2014.

This study was terminated by the sponsor [REDACTED] Following decision of [REDACTED] study termination all patients were called in for a last visit (documented on the final visit page of the case report form (CRF)).

Raw data listings, summary tables, graphs and statistical tests will be generated by means of the program SAS 9.3 or higher.

The following descriptive statistical parameters will be shown in summary tables

- Continuous variables: n (valid cases), n (missing data), mean, median, standard deviation (SD), min, max, quartiles
- Categorical variables: Count and percentage of category. Percentages are routinely based on the total category count excluding the missing category if not otherwise mentioned. Percentages showing a rate relative to the total number of patients in this group are given in special tables (e.g. Adverse Event (AE) tables). Footnotes will specify the percent basis.

For continuous variables, if not otherwise specified, mean, median and quartiles will be reported to one decimal place greater than the precision of data as collected. Standard deviation will be

presented in two decimal place greater than the data and minimum/ maximum values will be reported with the same precision, as they were collected. This rule is only valid if values are not converted for the summary.

Generally, percentages will be displayed in the format xx.d, i.e. one decimal place will be shown; if the calculated percentage is 100, no decimal is required (i.e. 100% and not 100.0%). If the count is zero no percentage needs to be shown.

2.2 Study objectives

The primary objective of this study is to evaluate the long-term effect of growth hormone treatment on the development of diabetes in short children born SGA for 10 years after the end of treatment.

The secondary objectives of this study are:

- to report the incidence of anti-rhGH antibodies 6 months after termination of growth hormone treatment
- evaluate final height in follow-up period
- to evaluate IGF-I and IGFBP-3 levels for 10 years after end of growth hormone treatment
- to evaluate incidence and severity of adverse events

2.3 Endpoints

2.3.1 Primary Endpoint

The development of diabetes is the primary endpoint of the study and is evaluated on the basis of the carbohydrate metabolism (fasting plasma glucose (FPG) and oral glucose tolerance test (OGTT)).

Specifically of interest is, number and percentage of patients developing overt type II diabetes mellitus after the end of GH treatment, characterized by fulfilment of the following criteria:

- FPG \geq 126 mg/dl (7.0 mmol/l) during blood sampling and/or during OGTT
- 2-h plasma glucose \geq 200 mg/dl (11.1 mmol/l) during OGTT

Documented confirmation on diagnosis of diabetes mellitus by investigator during OGTT will also be considered to qualify incidence of elevated glucose values as development of overt type II diabetes mellitus.

Fasting plasma glucose as well as an OGTT will be measured at baseline (i.e. final visit of EP00-401), 6 months, 1, 5 and 10 years after the end of treatment.

Additional criteria – carbohydrate metabolism

Additionally, long term effect of growth hormone (GH) treatment on carbohydrate metabolism is also assessed by

- Change from baseline in FPG, baseline and 2hr plasma glucose (during an OGTT), fasting plasma insulin and glucose glycosylated hemoglobin (HbA_{1C}) at 6 months, 1, 5 and 10 years after the end of treatment.

- **Insulin resistance** will be estimated at baseline, 6 months, 1, 5 and 10 years after the end of treatment, using both the homeostasis model assessment (HOMA; Matthews et al. 1985) and quantitative insulin sensitivity check index (QUICKI; Katz et al. 2000):

$$\text{HOMA} = \frac{\text{fasting insulin } (\mu\text{U/ml}) \times \text{fasting glucose (mg/dl)}}{405.41^*}$$

*use constant 22.5 instead of 405.41 if glucose concentration is reported in mmol/L

$$\text{QUICKI} = \frac{1}{\log \text{fasting insulin } (\mu\text{U/ml}) + \log \text{fasting glucose (mg/dl)}}$$

Implausible insulin or glucose values will be excluded, i.e. Glucose values below 0.1 mmol/L and insulin values below 0.1 pmol/L will not be used for the calculation of HOMA and QUICKI.

Potential of GH-treatment induced insulin resistance will be captured through change from baseline in HOMA and QUICKI at 6 months, 1, 5 and 10 years after the end of treatment

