4.6 Analysis of primary endpoint

Patients in the safety set (SAF) are considered for analyzing the primary endpoint (and related endpoints).

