4.6.1 Developing type II diabetes mellitus

Development of type II diabetes mellitus is the primary outcome measure, characterized by fulfilment of the following criteria:

- FPG \geq 126 mg/dl (7.0 mmol/l) during blood sampling and/or during OGTT
- 2-h plasma glucose \geq 200 mg/dl (11.1 mmol/l) during an OGTT
- Investigator documenting diagnosis of diabetes mellitus during OGTT

Accordingly, if lab values are elevated (both 2-hr plasma glucose and FPG) above the specified threshold for overt diabetes and investigator confirms with 'Yes' (question on OGTT page), consider the case for diabetes. But in case, 2-hr plasma glucose is elevated (overt) and FPG is normal/ impaired then investigator's response on diagnosis of diabetes will be considered only.

No inferential statistics is planned for this endpoint and results will only be interpreted in a descriptive manner.

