4.9 Analyses during an ongoing study

No interim analysis was finalized when the study was prematurely terminated.

5 References for SDS calculations

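### Written after early termination, the SAP still summarises its primary diabetes endpoint only as a number and percentage, with no patient-year rate and no confidence interval

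*SAP*

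**What the plan says.** Section 2.2 sets the primary objective as the "development of diabetes in short children born SGA for 10 years after the end of treatment". Early termination was known when the SAP was written. Section 2.1 reports the sponsor's termination in the past tense and says that patients were then called in for a closing visit. Section 4.9 states: "No interim analysis was finalized when the study was prematurely terminated".

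For the primary endpoint, section 2.3.1 names the "number and percentage of patients developing overt type II diabetes mellitus after the end of GH treatment". Fasting glucose and OGTT "will be measured at baseline (i.e. final visit of EP00-401), 6 months, 1, 5 and 10 years after the end of treatment". Section 4.6 assigns the analysis to the safety set. Section 4.6.1 gives the case definition (glucose thresholds and the investigator's answer on the OGTT page) and closes: "No inferential statistics is planned for this endpoint and results will only be interpreted in a descriptive manner". The standard categorical output in section 2.1 is a count and percentage. No confidence interval is named anywhere in the SAP.

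Follow-up time is nevertheless available. Section 4.5.2 derives and summarises each patient's study exposure, and section 4.7.1.3 uses months of exposure to give adverse event rates per patient-year.

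**The concern.** The objective is defined by a length of time, but the planned summary is tied neither to time at risk nor to precision. Section 2.6 admits a patient to the safety set on one visit after F0 or one adverse event, so there is no minimum follow-up. Termination also means that patients may have left at different times since baseline. The same percentage can therefore stand for quite different rates.

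The study exists to describe diabetogenic potential in the long term. Cases may be few or absent. A bare small count says nothing about the upper end of the risk that the data still allow, and a zero could be read as no risk.

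The denominator is also not firmly fixed. Section 4.6 points to the safety set, while the default in section 2.1 leaves missing values out of percentages unless stated otherwise.

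**Working it through.** The SAP gives no sample size, expected diabetes rate, termination date or follow-up distribution, so it has no figure to reproduce. All numbers below are illustrations. The patient number N, case count x, mean follow-up and 10-year risk are assumptions, shown over ranges.

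**1. Same percentage, different rate.** Person-years = N × mean follow-up; rate = 1000·x / person-years. The exact Poisson 95% limits for the count are χ²(0.025; 2x)/2 and χ²(0.975; 2x+2)/2. These are 0.025 and 5.57 for x = 1, and 0 and 3.69 for x = 0. With N = 100:

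| Mean follow-up (years) | Person-years | 1 case: percentage | 1 case: rate per 1000 (95% CI) | 0 cases: upper limit per 1000 |
|---|---|---|---|---|
| 3 | 300 | 1.0% | 3.3 (0.08–18.6) | 12.3 |
| 5 | 500 | 1.0% | 2.0 (0.05–11.1) | 7.4 |
| 7 | 700 | 1.0% | 1.4 (0.04–8.0) | 5.3 |
| 10 | 1000 | 1.0% | 1.0 (0.03–5.6) | 3.7 |

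The percentage column does not move, while the rate and its limits change by a factor of 10/3. With 0 cases at 5 years, the upper limit is 14.8, 7.4 or 3.7 per 1000 for N = 50, 100 or 200.

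**2. Percentage against the 10-year risk.** Assume a 10-year risk of 2% and a constant hazard: λ = −ln(0.98)/10 = 0.00202 per year, and F(t) = 1 − exp(−λt). Then F(3) = 0.60%, F(5) = 1.01% and F(7) = 1.40%. The expected share of the 10-year risk seen by 5 years is 0.50. It becomes 0.71 with a Weibull hazard of shape 0.5 and 0.25 with shape 2. The shortfall thus depends on a hazard shape that the SAP does not give.

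**3. Chance of few or no cases.** With everyone followed for 5 years under the constant hazard, the binomial probabilities are:

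| N | P(0 cases) | P(observed percentage ≥ 2%) |
|---|---|---|
| 50 | 0.60 | 0.40 |
| 100 | 0.36 | 0.27 |
| 200 | 0.13 | 0.14 |

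A zero count is a realistic outcome on these assumptions. The last column shows that the shortfall in step 2 holds in expectation only.

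**4. Does the wide visit spacing spoil a rate?** Take 1 case in 100 patients, the other 99 followed for 5 years. Diagnosis at year 1, 3 or 5 gives 495 + 1 = 496, 498 or 500 person-years, and rates of 2.02, 2.01 or 2.00 per 1000. With few cases, the diagnosis date hardly matters.

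**The case against.** The strongest reply is that this is a declared descriptive analysis. The SAP never calls the percentage a 10-year risk, and section 2.3.1 ties it only to the time after treatment. That is right, and it rules out saying that the SAP mislabels its estimate. It does not remove the gap, because the objective still names 10 years. A rate with an interval tests no hypothesis, although it does go beyond the output now planned.

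The second reply is that other outputs help. Diabetes reported as an adverse event would get a patient-year rate by preferred term (4.7.1.3). Visit counts (4.2), the exposure summary (4.5.2) and dated OGTT listings (4.6.2) allow an approximate rate. So it would be wrong to infer that the SAP leaves diabetes wholly unrelated to time. But the adverse event rate counts reported events rather than cases on the definition in section 4.6.1, and it has no interval. The other outputs leave the calculation to the reader.

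Three stronger readings are tempting and not supported:

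- *The reported percentage must lie below the 10-year risk.* This is so in expectation only; an observed percentage can equal or exceed it.
- *The rule "If the count is zero no percentage needs to be shown" hides a null result.* It is a display convention: the count of 0 is still shown, and the rule does not govern rates or intervals.
- *Showing the 10-year/final page as one EOS column (4.1) conceals the truncation.* The column is labelled as a termination visit, and exposure is summarised. Only the time since baseline beside those tables is missing, which is minor.

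**Conclusion.** The point holds as a gap in the planned summary that should be fixed, not as an invalid analysis. The primary endpoint has neither a person-time rate nor an interval, in a SAP that knows the study ended early, holds the follow-up time and plans patient-year rates for adverse events. The percentage cannot be read as the 10-year risk that the objective concerns, and with few or no cases it carries no statement of the remaining uncertainty.

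Confidence in the textual gap is high. The size of its effect in this trial cannot be stated, since neither patient numbers nor actual follow-up are in the text.

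**What to change.** In section 4.6.1, keep the number and percentage, state the denominator, and replace the closing sentence with wording such as:

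> No hypothesis test is planned. New cases per 1000 patient-years will be given with an exact Poisson 95% confidence interval, also when the count is zero. Patients who meet the definition at baseline are excluded and reported separately. Person-time runs from baseline (section 4.1) to first diagnosis or, without a diagnosis, to the last post-baseline glycaemic assessment. The number of SAF patients with no such assessment is shown, as they contribute no person-time. Because the study was terminated early, the percentage does not estimate the 10-year risk.

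As a minor addition, show n and the distribution of time since the same baseline beside the EOS tables. One time origin then serves both outputs.

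The cost is SAP wording, a few added lines in the primary table and one row block beside the EOS tables. These use dates and assessments the SAP already plans to hold, so no new data are needed. The downsides belong in a footnote: the interval will be wide with few cases, and a single rate averages over any change in risk with time.

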4.6.2 Additional criteria - carbohydrate metabolism

Absolute values as well as absolute and relative changes from baseline for fasting plasma glucose, OGTT parameters, fasting insulin, and HbA_{1c} values will be summarized descriptively by visit.

The effect of Omnitrope[®] treatment on HOMA and QUICKI scores, calculated subsequent for each plasma glucose and insulin measurement, will be evaluated at each visit using descriptive statistics for the observed values along with the absolute and relative changes from baseline.

HbA_{1c}, glucose and insulin data will be listed per parameter, center and patient number and will include: visit, sample date/day, fasting status, parameter result in CRF and SI unit, reference range in CRF and SI unit, outside reference range indicator, clinical significance and a column containing comments. Results of OGTT will be listed by center, patient number and will include: visit, sample date/day, fasting glucose at baseline (-10 minutes) and at 120 minutes in CRF and SI unit, a column providing if diabetes mellitus was diagnosed during OGTT, and comments. Assessed HOMA and QUICKI scores will be listed by center, patient number and visit. Additionally, fasting status and sample date/day will be provided.

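### The exclusion limits for HOMA and QUICKI do not screen out implausible insulin and glucose values, so single bad values can distort the means, SDs and mean changes

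*SAP*

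**What the plan says.** SAP section 2.3.1 defines HOMA and QUICKI and cites the source of the second as "quantitative insulin sensitivity check index (QUICKI; Katz et al. 2000". QUICKI is the reciprocal of the sum of the logarithms of fasting insulin (µU/ml) and fasting glucose (mg/dl); the base of the logarithm is not given. For HOMA the reader is told to "use constant 22.5 instead of 405.41 if glucose concentration is reported in mmol/L".

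The screening rule begins "Implausible insulin or glucose values will be excluded, i.e. Glucose values below 0.1 mmol/L", and its limits in full are "Glucose values below 0.1 mmol/L and insulin values below 0.1 pmol/L will not be used for the calculation of HOMA and QUICKI". The wording after the comma defines what counts as implausible, so the two floors are the whole rule. The SAP gives no upper limit, no limit on the computed index, and no instruction for a zero or negative logarithm sum.

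Section 4.6.2 says both indices "will be evaluated at each visit using descriptive statistics for the observed values along with the absolute and relative changes from baseline". Section 2.1 fixes the summary statistics: "Continuous variables: n (valid cases), n (missing data), mean, median, standard deviation (SD), min, max, quartiles". Section 4.1 says some laboratory results will be converted to common units.

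**The concern.** A plausibility filter should remove values that cannot be real measurements, and unit or decimal errors are an obvious source where results are converted between units. The glucose floor is one-seventieth of the SAP's own diabetes threshold for fasting glucose, "126 mg/dl (7.0 mmol/l) during blood sampling and/or during OGTT" (7.0 / 0.1 = 70).

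QUICKI is especially exposed because it is a reciprocal of a logarithm: it has no finite value where insulin times glucose equals 1, and it is negative below that. If that region lies inside the permitted range, the rule lets through results that have no meaning as an index of insulin sensitivity. Change from baseline in HOMA and QUICKI is the SAP's chosen measure of insulin resistance, and a bad baseline value enters that patient's change at every later visit.

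**Working it through.** **Inputs from the SAP.** Floors: glucose 0.1 mmol/L, insulin 0.1 pmol/L. HOMA constants: 405.41 (mg/dl) and 22.5 (mmol/L).

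**Assumptions.** Base-10 logarithm; insulin conversion f = 6.0 to 6.945 pmol/L per µU/ml; comparison pair of insulin 60 pmol/L and glucose 5 mmol/L; between-patient SD of QUICKI 0.035; 100 patients at a visit. The SAP gives none of these.

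**The SAP's own figure.** 405.41 / 22.5 = 18.018 mg/dl per mmol/L. The two HOMA constants agree with each other, and this factor is used below.

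**Formulas.** Product P = (insulin / f) × (glucose × 18.018). QUICKI = 1 / log10(P). HOMA = (insulin / f) × glucose in mmol/L / 22.5.

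**Where QUICKI breaks down.** P = 1 with insulin at its floor requires glucose = f / (0.1 × 18.018), which is 3.33 mmol/L (f = 6.0) to 3.85 mmol/L (f = 6.945). Both are far above the glucose floor, so the singular point lies inside the permitted range.

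**QUICKI at permitted values.**

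| Insulin (pmol/L) | Glucose (mmol/L) | P | QUICKI |
|---|---|---|---|
| 0.1 | 0.1 | 0.026 to 0.030 | -0.63 to -0.66 |
| 0.1 | 5 | 1.30 to 1.50 | 8.8 to 5.7 |
| 0.15 | 5 | 1.95 to 2.25 | 3.5 to 2.8 |
| 0.5 | 5 | 6.5 to 7.5 | 1.23 to 1.14 |
| 1 | 5 | 13.0 to 15.0 | 0.90 to 0.85 |
| 60 | 5 | 778 to 901 | 0.346 to 0.338 |

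**Effect of one such value on the mean.** Shift = (QUICKI of the bad value - usual QUICKI) / n. With n = 100:

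- insulin 0.1 pmol/L: (5.66 - 0.34) / 100 = 0.053, up to (8.85 - 0.35) / 100 = 0.085;
- insulin 0.15 pmol/L: (2.84 - 0.34) / 100 = 0.025, up to (3.46 - 0.35) / 100 = 0.031, or 7% to 9% of the usual value;
- insulin 1 pmol/L: about 0.005.

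The shift is inversely proportional to n, so it doubles at 50 patients and halves at 200.

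**Effect on the SD.** SD² = (98 × 0.035² + 0.99 × (bad - usual)²) / 99. For insulin 0.1 pmol/L the SD rises from 0.035 to 0.53 (f = 6.0) or 0.85 (f = 6.945).

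**Unit errors in glucose, with insulin 60 pmol/L.**

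- 90 mg/dl labelled mmol/L: HOMA = (60 / f) × 90 / 22.5 = 40.0 to 34.6, against 2.2 to 1.9 for the correct unit. The mean of 100 patients rises by about 0.33 to 0.38. QUICKI falls only to about 0.24.
- 5 mmol/L labelled mg/dl: converts to 5 / 18.018 = 0.28 mmol/L, which is above the floor. HOMA becomes 0.12 to 0.11 instead of about 2; QUICKI becomes 0.59 to 0.61.

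Both errors pass the stated rule.

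**The case against.** The case on the other side has force on consequence rather than on the rule itself.

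- Section 2.1 reports the median and quartiles next to the mean, and these barely respond to one value. The minimum and maximum would display a negative QUICKI or one of 5. This stands: a reader might infer that the SAP offers no robust summary, and that is not so.
- Section 4.6.2 lists glucose and insulin with reference ranges and an out-of-range flag, and lists the indices by patient and visit. Section 4.3 mentions a data review meeting before database lock. A gross error may well be noticed, and unit queries may be covered in data-management documents that are not shown. This also stands, but the tables would still be produced under the stated rule, which gives no basis for removing the value once seen.
- A reader might infer that any low value can overwhelm mean QUICKI. The figures do not support that: the strong effect needs insulin of about 0.1 to 0.5 pmol/L, and at 1 pmol/L with glucose 5 mmol/L it is slight.
- A reader might also blame the missing upper limit for the QUICKI problem. High values compress QUICKI; the missing ceiling mainly harms HOMA.
- Both indices are additional, descriptive criteria, and fasting glucose and insulin are summarised directly as well.

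**Conclusion.** The point holds as a minor one. The rule in section 2.3.1 does not exclude implausible values. It permits pairs at which QUICKI is undefined, negative or some 16 to 26 times its usual size, and it passes glucose unit errors in both directions. One such value can distort the mean, SD, minimum or maximum and mean change at a visit: about 0.03 or more in mean QUICKI for insulin of 0.15 pmol/L or less at glucose 5 mmol/L with 100 patients, and about 0.3 to 0.4 in mean HOMA for the high-side glucose error.

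The sizes rest on the assumed logarithm base, insulin conversion, comparison values and number of patients. The breakdown of QUICKI inside the permitted range holds at both ends of the conversion range. The SAP cannot show whether such values occur in the data. It would be wrong to infer a threat to the diabetes endpoint, which is not derived from HOMA or QUICKI.

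**What to change.** Before database lock, replace the two floors in section 2.3.1 with:

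1. two-sided plausibility limits for both glucose and insulin. For glucose, 2 to 40 mmol/L would serve as a data-cleaning assumption; the insulin limits should be set with the laboratory, since the SAP gives no basis for a figure;
2. a minimum product for QUICKI: do not calculate it when insulin (µU/ml) × glucose (mg/dl) is at or below, for example, 10. QUICKI then stays below 1, and one admitted value shifts a mean of 100 patients by less than (1 - 0.34) / 100 = 0.007. At glucose 5 mmol/L this sets aside only insulin at or below 10 / 90.1 = 0.111 µU/ml, or 0.67 to 0.77 pmol/L;
3. a query for unit errors on every flagged value first, then a listing of those excluded;
4. the base of the logarithm in QUICKI.

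Insulin should not be dropped merely because it is below the assay's quantification limit: that selectively removes patients with low insulin and pushes mean HOMA upward. State a substitution rule instead, in line with section 4.8, which retains low values for IGF-I, IGFBP-3 and the laboratory groups it names but does not mention insulin.

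The cost is a few sentences and one data check. The downside is that a few extreme but genuine values may be set aside; the listing keeps them visible.
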